NON-INTERVENTIONAL (NI) STUDY PROTOCOL

PASS information

Title	An Active Surveillance Study to Monitor the Real-World Long-term Safety of Somatrogon Among Paediatric Patients in Europe	
Protocol number	C0311023	
Protocol version identifier	2.0	
Date	20 March 2023	
EU Post Authorisation Study (PAS) register number	Study to be registered before the start of data collection	
Active substance	Somatrogon	
Medicinal product	Ngenla	
Product reference	EU/1/21/1617/001 for 24 mg/1.2 mL solution for injection in pre-filled pen	
	EU/1/21/1617/002 for 60 mg/1.2 mL solution for injection in pre-filled pen	
Procedure number	EMEA/H/C/005633	
Marketing Authorisation Holder (MAH)	Pfizer Europe MA EEIG [name]	
Joint PASS	No	
Research question and objectives	The primary research question for this study is: What is the long-term safety in paediatric patients treated with somatrogon in realworld routine clinical practice?	
	Primary Objective: Estimate the incidence rates of neoplasms, and diabetes mellitus	

PFIZER CONFIDENTIAL

type 2, the primary safety events of interest in paediatric patients treated with somatrogon, and paediatric patients treated with once daily somatropin, in the course of routine clinical care.

Secondary Objectives:

- a) Estimate the incidence rates of clinical endpoints related to immunogenicity, medication errors, the secondary safety events of interest, in paediatric patients treated with somatrogon, and paediatric patients treated with once daily somatropin, in the course of routine clinical care.
- b) Evaluate long-term efficacy by measuring insulin-like growth factor-1 (IGF-1) levels, and height in paediatric patients treated with somatrogon, and paediatric patients treated with once daily somatropin, in the course of routine clinical care
- c) Estimate the hazard ratios of neoplasms, and diabetes mellitus type 2, the primary safety events of interest, between paediatric patients treated with somatrogon, and paediatric patients treated with once daily somatropin, in the course of routine clinical care.
- d) Estimate the hazard ratios of the clinical endpoints related to immunogenicity, the secondary safety events of interest, between paediatric patients treated with somatrogon, and paediatric patients treated with once daily somatropin, in the course of routine clinical care.

Countries of study	France, Spain, Sweden, and the UK

2. LIST OF ABBREVIATIONS

Abbreviation	Definition	
AE	Adverse event	
ATC	Anatomical Therapeutic Chemical	
CIP	Code Identifiant de Présentation (Presentation ID Code)	
CNAM	Caisse Nationale d'Assurance Maladie (French National Health Insurance Fund)	
CNIL	National Commission for Data Protection in France	
DRG	Diagnosis-related group	
EMA	European Medicines Agency	
EMR	Electronic Medical Records	
ENCePP	European Network of Centres for Pharmacoepidemiology and Pharmacovigilance	
EU	European Union	
GDPR	General Data Protection Regulation	
GH	Growth hormone	
GHD	Growth hormone deficiency	
GP	General practitioners	
GPP	Good Pharmacoepidemiology Practices	
hGH	Human growth hormone	
HR	Hazard ratio	
HV	Height velocity	
ICD	International Classification of Diseases	

Abbreviation	Definition		
ICH	International Council for Harmonisation		
IEC	Independent Ethics Committee		
IGF-1	Insulin-like growth factor-1		
INE	Instituto Nacional de Estadística (Institute of National Statistics)		
IRB	Institutional Review Board		
LPD	Longitudinal Patient Database		
NBHW	National Board of Health and Welfare		
NHS	National Health Service		
PAS	Post-Authorisation Studies		
PASS	Post-Authorisation Safety Study		
PIN	Personal Identification Number		
PMSI	Programme de médicalisation des systèmes d'information (French National Hospital Discharge Database)		
QC	Quality control		
QMS	Quality Management System		
SAP	Statistical Analysis Plan		
SDS	Standard deviation score		
SLSP	System level security policy		
SNDS	Système National des Données de Santé (French administrative healthcare database)		
SOP	Standard operating procedure		
TBD	To be determined		

PFIZER CONFIDENTIAL

Abbreviation	Definition
THIN	The Health Improvement Network
UCD	Unité Commune de Dispensation (Smallest Unit of Dispensation)
UK	United Kingdom

4. ABSTRACT

Full Study Title: An Active Surveillance Study to Monitor the Real-World Long-term Safety of Somatrogon Among Paediatric Patients in Europe

Protocol version: 2.0, 20 March 2023

Main Author: [name], Pfizer Inc., [name]

Rationale and Background:

Human growth hormone (hGH) is a 191-amino-acid pituitary protein that stimulates production and release of insulin-like growth factor-1 (IGF-1). Growth hormone (GH) and IGF-1 are the primary mediators of the promotion of growth in paediatric individuals and play a role in the regulation of body composition and metabolism in paediatric individuals and adults. Growth hormone deficiency (GHD) results in inadequate production of IGF-1, which together with insufficient direct effects of GH subsequently results in abnormal linear growth in children. Paediatric patients affected with GHD have been treated with daily administration of recombinant hGH replacement therapy for many years which is proven to be effective and have a good short-term safety profile; [Pfäffle et al 2013; Lundberg et al 2020] subsequently, hGH has been approved in many countries around the world for other conditions associated with growth failure and/or abnormal body composition. However, the burden of daily administration and its concomitant side effects (eg injection site discomfort and arthralgia) may cause a reduction in compliance and limit the therapeutic utility of existing formulations.

Somatrogon (PF-06836922, also referred to as MOD-4023) is a long-acting once-weekly subcutaneously-administered form of hGH (marketing authorisation granted in the EU in February 2022 and UK in March 2022) developed for the treatment of children and adolescents from 3 years of age with growth disturbance due to insufficient secretion of GH. Yet, there is limited literature to date on the long-term sequelae of prolonged hGH use.[Pfäffle et al 2013; Lundberg et al 2020] The mitogenic properties of mediators in the GH pathway, as well as prior evidence to suggest an association between impairment of glucose metabolism and recombinant hGH use, merit a need to fill a gap on understanding long-term safety outcomes for GHD therapy.

The primary purpose of this study will be to assess the long-term safety of somatrogon, a long-acting hGH, under routine clinical care and is intended to reflect outcomes that occur in real-world clinical practice.

This non-interventional study is designated as a Post-Authorisation Safety Study (PASS) and is a commitment to the EMA.

Research Question and Objectives:

The primary research question for this study is: What is the long-term safety in paediatric patients treated with somatrogon in real-world routine clinical practice?

Primary Objective:

Estimate the incidence rates of neoplasms, and diabetes mellitus type 2, the primary safety events of interest in paediatric patients treated with somatrogon, and paediatric patients treated with once daily somatropin, in the course of routine clinical care.

Secondary Objectives:

- a) Estimate the incidence rates of clinical endpoints related to immunogenicity, medication errors, the secondary safety events of interest, in paediatric patients treated with somatrogon, and paediatric patients treated with once daily somatropin, in the course of routine clinical care.
- b) Evaluate long-term efficacy by measuring IGF-1 levels, and height in paediatric patients treated with somatrogon, and paediatric patients treated with once daily somatropin, in the course of routine clinical care.
- c) Estimate the hazard ratios of neoplasms, and diabetes mellitus type 2, the primary safety events of interest, between paediatric patients treated with somatrogon, and paediatric patients treated with once daily somatropin, in the course of routine clinical care.
- d) Estimate the hazard ratios of the clinical endpoints related to immunogenicity, the secondary safety events of interest, between paediatric patients treated with somatrogon, and paediatric patients treated with once daily somatropin, in the course of routine clinical care.

The safety events of interest noted above, are based on the current understanding of the important potential risks associated with somatrogon. However, other endpoints may be added as understanding of the safety profile of somatrogon evolves and feasibility of their assessment permits.

Study Design:

This is a population-based cohort study using routinely collected electronic healthcare data in France, Spain, Sweden, and the United Kingdom (UK). The study population will be comprised of paediatric patients (ie, patients from 3 years to below the age of 18) receiving once weekly somatrogon following registration of the product in the European Union (EU) and UK, and an internal comparator population of paediatric patients treated with daily somatropin accrued during the same time period as the somatrogon treated patients.

Population:

The source population for this study will be comprised of paediatric patients contributing data to the 4 electronic healthcare databases. The active surveillance population includes all

paediatric patients receiving at least 1 somatrogon prescription/dispensing during the study accrual period. The study will also include an internal comparator population of paediatric patients receiving at least 1 prescription/dispensing of once daily somatropin during the study accrual period. Additionally, patients in all databases will have 12 months (depending on feasibility that will be assessed before the end of data collection, this may be reduced to 6 months) of continuous medical history available prior to the index date (defined as start of somatrogon or once daily somatropin within the study period of February 2022 to February 2032) to allow for adequate capture of baseline characteristics.

Study follow-up will span a 10-year study period, throughout which patients can accrue and will be evaluated in two stages. First, patients will be accrued within the first 5 years and followed for a minimum of 5 and up to 10 years to evaluate long-term safety events of interest. Second, in sensitivity analyses, all patients that accrue after the 5-year mark, will be analysed both separately and together with the study population.

Variables:

- Exposure:
 - ≥1 somatrogon prescription/dispensing during study accrual period.
 - \circ \geq 1 prescription/dispensing of once daily somatropin during study accrual period (for the internal comparator group).
- Outcomes: The primary outcomes of interest are neoplasms and diabetes mellitus 2. The secondary outcomes of interest are immunogenicity, medication errors, and long term efficacy characterized by IGF-1 levels and height.
- Key covariates: patient demographics and clinical characteristics, measured risk factors, co-morbidities, concomitant medications at baseline and co-medications during follow-up.

Data Sources: The study will be performed in the following selected data sources:

- France Système National des Données de Santé (SNDS; an administrative claims database covering approximately 66 million in the population)
- Spain –Longitudinal Patient Database (LPD; a longitudinal patient data based on electronic medical records covering approximately 1 million individuals in the population)
- Sweden the Total Population Register, Patient Register, the Swedish Prescribed Drug Register, and the National Swedish Growth Hormone Registry. The Swedish register systems are a large source of population-based data (covering approximately 10 million)

• UK – The Health Improvement Network (THIN) database; an electronic primary healthcare records database (covering approximately 20 million)

Study Size:

All somatrogon-treated paediatric patients in all data sources during the study accrual period will be included in the study. Preliminary feasibility assessment of data in the Swedish nationwide and regional registers from 2008 to 2019 indicates that there were approximately 4,000 patients treated with somatropin per year with 1700 patients estimated to be paediatric patients. In the UK THIN database from 1995-2020, there were approximately 3,375 patients treated with somatropin with 20% (650 patients) estimated to be paediatric patients. In Spain, from 2013-2022, there were approximately 700 patients treated with somatropin, from which 642 received a first dose as pediatric patients. Similar information from France was unavailable. Based on incidence rates of the primary safety events of interest in somatropin treated paediatric patients from previous GHD studies, the range of person-years of somatropin exposure needed to observe one event for neoplasms and diabetes is estimated to be 1,124 to 62,500. Comparative analyses for neoplasms will be performed if there are ≥1,305 patients in the somatrogon-treated group, which would allow for an HR of 3.00 or higher to be detected between somatrogon and once daily somatropin-treated groups. Comparative analyses for diabetes mellitus type 2 will be performed if there are $\geq 2,344$ patients in the somatrogon-treated group, which would allow for an HR of 3.00 or higher to be detected between somatrogon and once daily somatropin-treated groups.

Data analysis:

The primary analysis will be descriptive. All eligible patients during the study period will be included, with no upper limit on the sample size. Due to database heterogeneity, analyses will be conducted separately by data source and data will not be pooled.

Baseline demographic and clinical characteristics for each treatment group will be described. For all the safety events of interest and efficacy measurements of interest, descriptive statistics, counts and proportions, crude incidence rates (ie, number of events per person years) and age/sex standardized incidence rates with associated two-sided 95% confidence intervals will be calculated as appropriate.

The summary of event rates will be based on survival analysis of time to first event based on an index date defined for each treatment group with appropriate censoring rules applied for those who do not experience an event by end of follow-up period including those who die, those who are lost to follow-up (eg, via migration out of the country as documented in the data source), or end of study period.

The feasibility of more formal comparative analyses to evaluate safety events of interest and obtain hazard ratios that adequately adjust for potential confounders will be assessed in the interim reports. Since the size of the once daily somatropin-treated comparator group is

expected to be much larger than the somatrogon-treated group, statistical power will be limited by the uptake of somatrogon.

Milestones: Data collection is planned to start on 15 June 2024 and end on 15 June 2032. The first interim report is planned to be submitted within three years of EU approval of somatrogon, taking into account the lag in data availability in respective data sources. Subsequent interim reports are planned for every 2 years thereafter. The final study report planned for submission will take place within 6 months from the end of data collection.

5. AMENDMENTS AND UPDATES

Amendment number	Date	Protocol section(s) changed	Summary of amendment(s)	Reason
1	07 March 2023	Cover page, Section 4 and Section 8	The research question has been revised to: "What is the long-term safety in paediatric patients treated with somatrogon in real-world routine clinical practice?"	EMA requested that the protocol research question be reworded to be in line with the purpose of the study, long-term safety.
1	07 March 2023	Section 4 and 7	The primary purpose has been revised to read: "The purpose of this study will be to assess the long-term safety of somatrogon, a long-acting hGH, under routine clinical care and is intended to reflect outcomes that occur in real-world clinical practice."	EMA requested that the primary purpose in the protocol be reworded to the primary purpose of the study as stated in the somatrogon RMP.
1	07 March 2023	Section 4 and Section 6	The planned dates for start and end of data collection, 4 interim reports, and final study report have been revised.	Milestone dates provided in the original protocol will be revised in collaboration with the EMA, to account for operational aspects of study implementation.

6. MILESTONES

Milestone	Planned date	
Registration in the EU PAS register	Prior to start of data collection	
Start of data collection ^a	15 June 2024	
End of data collection ^b	15 June 2032	
Interim report 1	15 December 2024	
Interim report 2	15 December 2026	
Interim report 3	15 December 2028	
Interim report 4	15 December 2030	
Final study report	15 December 2032	

EU: European Union; PAS: post authorisation study.

a. For studies with secondary data collection, the start of data collection is defined as the planned date for starting data extraction for the purposes of the primary analysis.

b. For studies with secondary data collection, the end of data collection is defined as the planned date on which the analytical dataset will be first completely available; the analytic dataset is the minimum set of data required to perform the statistical analysis for the primary objective(s).

7. RATIONALE AND BACKGROUND

Human growth hormone (hGH) is a 191-amino-acid pituitary protein that stimulates production and release of insulin-like growth factor-1 (IGF-1). Growth hormone (GH) and IGF-1 are the primary mediators of the promotion of growth in paediatric individuals and play a role in the regulation of body composition and metabolism in paediatric individuals and adults. Growth hormone deficiency (GHD) results in inadequate production of IGF-1 which together with indirect effects of GH subsequently results in abnormal linear growth in children. Paediatric patients affected with GHD have been treated with daily administration of recombinant hGH replacement therapy, such as somatropin, for many years which is proven to be effective and have a good short-term safety profile; [Pfäffle et al 2013; Lundberg et al 2020] subsequently, hGH has been approved in many countries around the world for other conditions (eg, idiopathic short stature) associated with growth failure and/or abnormal body composition. However, the burden of daily administration and its concomitant side effects (eg, injection site discomfort and arthralgia) may cause a reduction in compliance and limit the therapeutic utility of existing formulations.

Somatrogon (PF-06836922, also referred to as MOD-4023) is a long-acting once-weekly subcutaneously-administered form of hGH (marketing authorisation granted in the EU in February 2022 and UK in March 2022) developed for the treatment of children and adolescents from 3 years of age with growth disturbance due to insufficient secretion of GH. Yet, there is limited literature to date on the long-term sequelae of prolonged hGH use.[Pfäffle et al 2013; Lundberg et al 2020] The mitogenic properties of mediators in the GH pathway, as well as prior evidence to suggest an association between impairment of gluose metabolism and recombinant hGH use, merit a need to fill a gap on understanding long-term safety outcomes for GHD therapy.

The primary purpose of this study will be to assess the long-term safety of somatrogon, a long-acting hGH, under routine clinical care and is intended to reflect outcomes that occur in real-world clinical practice.

This non-interventional study is designated as a Post-Authorisation Safety Study (PASS) and is a commitment to the EMA.

8. RESEARCH QUESTION AND OBJECTIVES

The primary research question for this study is: What is the long-term safety in paediatric patients treated with somatrogon in real-world routine clinical practice?

Primary Objective:

Estimate the incidence rates of neoplasms, and diabetes mellitus type 2, the primary safety events of interest in paediatric patients treated with somatrogon, and paediatric patients treated with once daily somatropin, in the course of routine clinical care.

Secondary Objectives:

- a) Estimate the incidence rates of clinical endpoints related to immunogenicity, medication errors, the secondary safety events of interest, in paediatric patients treated with somatrogon, and paediatric patients treated with once daily somatropin, in the course of routine clinical care.
- b) Evaluate long-term efficacy by measuring IGF-1 levels, and height in paediatric patients treated with somatrogon, and paediatric patients treated with once daily somatropin, in the course of routine clinical care.
- c) Estimate the hazard ratios of neoplasms, and diabetes mellitus type 2, the primary safety events of interest between paediatric patients treated with somatrogon, and paediatric patients treated with once daily somatropin, in the course of routine clinical care.
- d) Estimate the hazard ratios of the clinical endpoints related to immunogenicity, the secondary safety events of interest, between paediatric patients treated with somatrogon, and paediatric patients treated with once daily somatropin, in the course of routine clinical care.

The safety events of interest noted above, are based on the current understanding of the important potential risks associated with somatrogon. However, other endpoints may be added as understanding of the safety profile of somatrogon evolves and feasibility of their assessment permits.

9. RESEARCH METHODS

9.1. Study design

This is a population based cohort study using routinely collected electronic healthcare data in France, Spain, Sweden, and the UK, during a study period of February 2022 to February 2032. Table 1 summarizes these data sources and their capabilities of addressing research objectives. The study population will be comprised of paediatric patients (ie, patients from 3 years to below the age of 18) who initiate once weekly somatrogon following registration of the product in the EU and UK, and an internal comparator population of paediatric patients who initiate treatment with daily somatropin accrued during the same time period as the somatrogon treated patients.

Table 1. Summary of study objectives and country-specific databases that have data to address them.

	Système National des Donnees de Sante (SNDS)	Longitudinal Patient Database (LPD) in Spain	Sweden Growth Hormone Registry and national health and demographic registers	The Health Improvement Network (THIN)
Primary objective	yes	yes	yes	yes
Secondary objective 2a	yes*	yes	yes	yes***,†
Secondary objective 2b	no	no	yes	no
Secondary objective 2c	yes	yes	yes	yes
Secondary objective 2d	yes**	yes	yes	yes [†]

^{*}not for medication errors as weight is not collected in this database.

† not for all immunogenicity clinical endpoints.

9.2. Setting

9.2.1. Inclusion criteria

Patients must meet all of the following inclusion criteria to be eligible for inclusion in the study:

• All paediatric (from 3 years to below the age of 18 years) patients receiving at least 1 somatrogon prescription/dispensing or at least 1 prescription/dispensing of daily somatropin during the study accrual period.

^{**}for hospitalized outcomes only.

^{***}medication error accuracy contingent on UK shared care between primary care physicians and secondary care providers.

• 12 months (depending on feasibility that will be assessed before the end of data collection, this may be reduced to 6 months) of continuous medical history available prior to the index date (defined as start of somatrogon or once daily somatropin within the study period) to allow for adequate capture of baseline characteristics.

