9.2.3. Index Date and Follow-Up

The index date will be the date of the first filled prescription/dispensing of somatrogon or once daily somatropin as recorded in the data sources. The patients will be followed from the index date to whichever of the following that occurs first:

- Primary or secondary safety event of interest (follow-up time will be from the index date to the date of the event, at which the patient will be censored for that particular event of interest. Follow-up will continue for the other safety events of interest)
- Death
- Lost to follow-up (eg, via migration out of the country as documented in the data source(s)), or
- End of the study follow-up

The study will span a 10-year study period, throughout which patients can accrue and will be evaluated in 2 stages. First, patients will be accrued within the first 5 years and followed for a minimum of 5 and up to 10 years to evaluate long-term safety events of interest, Figure 1. Second, in sensitivity analyses, all patients that accrue after the 5-year mark, and therefore, with less than 5 years of follow-up, will be analyzed both separately and together with the study population. (Section 9.7.2.4)

Figure 1. Patients Inclusion and Follow-up

Inclusion of patients prescribed/dispensed with at least 1 dose of somatrogon or once daily somatropin

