9.3. Variables

Operational definitions of the following variables will be described in the statistical analysis plan (SAP).

Exposure:

- First filled Somatrogon prescription/dispensing following registration of the product in EU and UK.
- For the internal comparator, first filled somatropin prescription during the same study period as somatrogon patients.

As noted above, operational definitions of exposure will be specified in the SAP (eg, if feasible and subject to sample size, by: somatrogon use, those who switch between somatrogon and somatropin, or somatropin use).

Outcomes

The following are the safety events of interest:

Primary-

- neoplasms
- diabetes mellitus type 2

Secondary-

• immunogenicity

Where feasible, to evaluate immunogenicity within the respective databases, the following clinical endpoints related to immunogenicity will be captured:

- o Bronchospasm
- Allergic conjunctivitis
- o Allergic dermatitis
- Atopic dermatitis
- Eyelid oedema
- Henoch-Schonlein purpura
- Hypersensitivity
- o Rash
- o Allergic rhinitis
- Swelling face
- Swelling of eyelid
- Urticaria
- Medication errors

Where feasible, to evaluate medication errors for somatrogon within the respective databases, utilizing prescription information and weight

measurements, the following endpoints related to medication errors will be captured:

- Underdosing defined as a:
 - 50% decrease in dose for a single administration (or, dispensing that is <0.33 mg/kg body weight)
 - o Missing a dose within the course of 2 weeks
- Overdosing defined as:
 - o 50% increase in dose for a single administration (or, dispensing that is >0.99 mg/kg body weight)
 - O An extra dose administration within 4 days of the last dose

(The recommended dose for somatrogon is 0.66 mg per kilogram of body weight via a single weekly injection, adjusted by the doctor if necessary.)

For somatropin, the recommended dose in mg per kilogram of body weight via a daily injection, will be manufacturer dependent. Analogous to somatrogon, underdosing and overdosing will be defined as a 50% decrease and increase in dose for a single administration, respectively.

• Long-term efficacy

Where feasible, to evaluate long-term efficacy within the Swedish Growth Hormone Registry database, the following endpoints related to long-term efficacy will be captured:

- o IGF-1 levels
- Height (height velocity (HV), height standard deviation score (SDS), change in height SDS, and final height).

Covariates:

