9.7.1. Subgroup Analysis

Patients will be initiating treatment of somatrogon (or somatropin, for the internal comparator group) during the study accrual period, but may have a history of using other recombinant hGH therapy, prior to study entry. As feasible, for the descriptive and comparative analysis (will only be performed at the time of the final report if the number of patients in the somatrogon-treated group would allow for an HR of 3.00 or higher to be detected with 80% power at the 5% significance level, assuming 0% annual switching between somatrogon and once daily somatropin-treated groups), a subgroup analysis among prevalent users of GH therapies and new users of GH therapies will be performed to quantify neoplasms and diabetes mellitus type 2 rates.

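### Sections 9.1, 9.2.1, 9.2.3 and 9.3 of the protocol give inconsistent rules for who enters the somatropin comparator and when follow-up starts, so children already on treatment may be mixed with starters

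*Protocol*

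**What the plan says.** The protocol describes comparator entry and time zero in several places:

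- Section 9.1 describes "paediatric patients who initiate treatment with daily somatropin accrued during the same time period" as the somatrogon patients.
- Section 9.2.1, first criterion, asks only for "at least 1 prescription/dispensing of daily somatropin during the study accrual period". The Population paragraph of the abstract repeats this rule. The age range of 3 to under 18 years sits in the same criterion, without a date at which it is judged.
- Section 9.2.1, second criterion, requires 12 months of history (possibly cut to 6) before an index date "defined as start of somatrogon or once daily somatropin within the study period". The stated purpose of that history is to capture baseline characteristics. The abstract adds the dates February 2022 to February 2032.
- Section 9.2.3: "The index date will be the date of the first filled prescription/dispensing of somatrogon or once daily somatropin as recorded in the data sources".
- Section 9.3 defines comparator exposure as the "first filled somatropin prescription during the same study period as somatrogon patients".

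Section 9.2.2 lists no exclusions. Section 9.7.1 accepts that patients may have used other recombinant growth hormone before entry and says that, as feasible, "a subgroup analysis among prevalent users of GH therapies and new users of GH therapies will be performed". Section 9.7 puts all eligible patients into the primary descriptive analysis, separately by data source and without pooling.

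**The concern.** Somatropin has a stock of children already on treatment when accrual opens; Section 9.5 puts it at about 1,700 in Sweden in 2019. Somatrogon has none, because it was authorised in February 2022 (EU) and March 2022 (UK). The conflict therefore falls essentially on one arm.

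If ongoing users enter at a mid-course refill, the comparator mixes children at the start of treatment with children who have been treated for years without stopping. Rates and hazard ratios then differ between arms whenever risk changes with time on treatment. If time zero is put back to a fill before February 2022, the comparator gains person-time during which the child had to stay alive and on treatment in order to qualify.

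Section 9.6 has investigators in each country generate or receive their own data, so different teams could follow different sentences. The primary objective consists of these rates, and crude and age/sex-standardised rates are not adjusted for prior treatment.

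**Working it through.** **Side-by-side test.** Take a child on somatropin since 2018 who refills in February 2022.

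| Protocol text | Enters? | Index date |
|---|---|---|
| 9.1 (initiates) | No | none |
| 9.2.1, first criterion; abstract | Yes | not stated there |
| 9.2.1, second criterion (start within the period) | No such start | none |
| 9.2.3 (first fill as recorded) | not stated there | 2018, if the records reach back |
| 9.3 (first fill in the study period) | Yes | February 2022 refill |

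These answers cannot all hold. Age is also open: a child who started at 2 and has a fill at 3 meets the age criterion, yet the first recorded fill was below the limit.

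**Illustration of size.** The protocol gives neither the share of ongoing users nor their prior treatment time, so both are assumed.

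Inputs from Section 9.5 (Table 4 assumptions): comparator neoplasm rate 0.9 per 1,000 person-years, 5-year uniform accrual, 10-year study, 5% annual loss in both arms. With these inputs a log-rank calculation gives 1,308 per arm for a hazard ratio of 3.00, against the stated 1,305. The sample size is not in question here.

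Let c = −ln(0.95) = 0.0513 and l = c + 0.0009 = 0.0522.

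- Mean follow-up, uniform accrual: f = [1 − (e^(−5l) − e^(−10l))/(5l)]/l = 6.17 years.
- Mean follow-up, entry on opening day: g = (1 − e^(−10l))/l = 7.79 years.
- With a share s of ongoing users, F = (1 − s)f + s·g.

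The true hazard ratio is set to 1 throughout.

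*Index at a fill before 2022.* Assume m prior years per ongoing user, all event-free. Observed comparator rate = 0.9·F/(F + s·m); apparent hazard ratio = (F + s·m)/F.

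- s = 0.25, m = 1: F = 6.57; rate 0.87; ratio 1.04.
- s = 0.50, m = 3: F = 6.98; rate 0.74; ratio 1.21.
- s = 0.75, m = 5: F = 7.39; rate 0.60; ratio 1.51.

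*Index at the first in-period refill.* Assume the hazard is k times baseline in the first 2 treatment years, ongoing users are past that window, and every somatrogon child is a new user. Person-years in the first 2 years: p = (1 − e^(−2c))/c = 1.90. Starter rate = 0.9·(k·p + f − p)/f. The comparator rate is the person-time-weighted mix of the starter rate and 0.9.

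| k | Starter rate | Comparator rate, s = 0.25 to 0.75 | Apparent ratio |
|---|---|---|---|
| 0.5 | 0.76 | 0.80 to 0.87 | 0.95 to 0.87 |
| 1 | 0.90 | 0.90 | 1.00 |
| 1.5 | 1.04 | 1.00 to 0.93 | 1.04 to 1.12 |
| 3 | 1.45 | 1.29 to 1.02 | 1.13 to 1.43 |

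Under the refill index the sign depends on k. There is no bias if the hazard is constant. The comparator looks too safe if risk is front-loaded, and too risky if events are delayed.

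**The case against.** The best defence is that the sections can be read together. Section 9.2.1 requires all criteria to be met, and its second criterion defines the index as a start within the study period. Section 9.1 speaks of initiation, and Section 9.7.1 says patients will be initiating treatment during accrual. Applied strictly, ongoing users drop out and neither bias arises from them. Section 9.3 leaves operational definitions to the SAP. Prior GHD therapy and duration of GHD are listed covariates, and Section 9.7.2.2 adds a 6-month lag.

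Part of this stands. A reader might infer that the comparator certainly carries immortal-time bias. The documents do not support that: an index before 2022 rests on Section 9.2.3 alone, and the abstract, the second criterion of 9.2.1, Section 9.3 and the 10-year follow-up ceiling in 9.2.3 itself all contradict it (a 2018 index would allow 14 years).

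A reader might also infer that the bias must run against somatrogon. That is not established. Somatrogon starters may themselves be experienced users (9.7.1), and delayed events (9.7.2.2, 9.9) could raise the comparator rate.

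Nor can the ongoing share be derived from Section 9.5. Person-years per enrolled child in the Table 2 footnotes (126,754/39,116 = 3.2; 192,345/54,996 = 3.5) are registry exposure, not treatment duration. Turning them into a share also presumes a steady state and that every ongoing user enters.

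The rest does not remove the point. Deferral to the SAP does not cure rules already fixed inconsistently, because any SAP must override at least one section. Covariate adjustment reaches only the conditional Cox model. A lag counted from a refill does not restore the start of treatment.

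**Conclusion.** The inconsistency is certain and can be read directly from the text; the resulting bias is possible. If ongoing somatropin users enter at a refill, the primary rates and any hazard ratio may carry prevalent-user bias. If a country team follows Section 9.2.3 literally, immortal person-time is added as well.

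The protocol does not allow the size or direction to be computed. The ranges in the working rest on assumed shares of 25 to 75%, assumed prior time of 1 to 5 years, an assumed early-hazard multiple and, for the early index, event-free prior time. That last assumption is weaker for an event that does not end treatment.

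The subgroup in Section 9.7.1 does not settle the matter. It is conditional on feasibility, leaves the main rates mixed, and cannot be built consistently until the index date is fixed. The rules should be reconciled before data extraction.

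**What to change.** Use one rule in Sections 9.1, 9.2.1, 9.2.3 and 9.3 and in the abstract:

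- The index date is the first fill, within the study period and never before February 2022, of somatrogon or of any somatropin brand, with no fill of that same substance in the look-back.
- The look-back covers all brands, so that a brand change does not count as a start. It has the same length as the continuous-history window (12 months, or 6 if that is reduced).
- Age is 3 to under 18 years on the index date.

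In Section 9.7.1, make the split by prior growth hormone use (naive or experienced) a committed stratification of the primary rates in both arms. Adjust or stratify any Cox model by it. Do not restrict the main analysis to naive children: that would remove switchers from the somatrogon arm, which limits power and must reach 1,305 or 2,344 patients per data source.

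The cost is wording in five places, one look-back query per database, and a smaller comparator. The smaller comparator is affordable, since Section 9.7 expects that group to be an order of magnitude larger than the somatrogon group.
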